#### 11.3.2.2 Sensitivity Analysis

None planned.

#### 11.3.2.3 Supplementary Analysis

None planned.

#### 11.4 Other Analyses

None planned.

#### 11.5 Interim Analysis

No formal interim analysis is planned.

#### 11.6 Sample Size Determination

Approximately 30 participants will be recruited. A single-group design will be used to obtain a two-sided 95% confidence interval for a single proportion of the RUAT Echo images that are deemed of sufficient quality. The Exact (Clopper-Pearson) formula will be used to calculate the confidence interval. The sample proportion is assumed to be 80%. With a sample size of 30, the width of the associated confidence interval is 30.9% around the 80% (that is, from 61.4% to 92.3%).

Confidence interval widths were computed using PASS 2023, version 23.0.2.

### 12 Risk Analysis

The Investigator Brochure provides information regarding the robotic system and a more detailed risk analysis (Refer Investigator Brochure Section # B 5). The devices used in this study have no interventional aspect. There are no known health risks associated with diagnostic ultrasound technology.

A summary of identified risks associated with participation in this study include:

**Risk: Study Participant discomfort due to pressing of ultrasound probe on chest (Robot-assisted Ultrasound Examination)**

Mitigation: Participants will be informed of the potential for slight discomfort on the chest from pressing the ultrasound probe and that they can discontinue participation at any point if they find the pressure from the probe too uncomfortable to continue participation. The robot has an active pressure sensor with a limiter to prevent excess pressure being applied. The pressure limit is set to approximately 50% of the maximum pressure exerted by a human operator performing a standard ultrasound examination. A blue LED light on the sensor confirms pressure signals are actively being received and in the event of sensor failure, the pressure reading will drop to zero. Daily checks of the system include a manual test of the

	QMS Template	Doc ID: RMI-ROBOTECHO-CIP-002 Ver No: V2.0
	Clinical Investigation Protocol	

pressure sensor which requires applying gentle pressure to the probe holder and the sonographer is to confirm that the force indicator moves on the computer display for every force limit level (1-5).

**Risk: Operation of a robot arm**

The RUAT holds and manipulates clinical and TGA approved ultrasound probes; the RUAT itself is controlled and always supervised by a human operator, and the supervising operator / attendant will always remain within 0.5m of the robot arm. The operator, the attendant and the patient all have an emergency stop button each within arm’s reach which terminates the robot action within approximately 1 second.

**Risk: Collection of confidential participant data**

All collected data will be de-identified. All active and working data documents are secured with automated tracking logging to monitor all user access and activity.

**13 Subject Completion and Discontinuation**

**13.1 Subject Replacement**

It is anticipated that all subjects will complete the study. If a subject withdraws during the study after receiving RUAT echocardiogram, they will not be replaced.

**13.2 Subject Withdrawals**

Subjects will be withdrawn from the study if:

- Their consent is withdrawn.
- In the investigator’s opinion, the subject’s clinical condition necessitates withdrawal for safety reasons.
- They are unable to tolerate RUAT echocardiogram procedure.

Subjects will be advised that they may voluntarily withdraw from the study at any time, for any reason and they are not obligated to reveal the reason to the sponsor, and it will not affect their medical care. However, in such cases, appropriate efforts will be made by the sponsor to determine the reason for voluntary withdrawal from the study.

Subjects will be informed that should they withdraw from the study they should remain in the care of an appropriately experienced physician until the physician deems further follow-up unnecessary.

A Study Completion Form will be completed for all patients who withdraw from the study.

**14 Study Termination**

The sponsor, investigator, HREC or TGA reserves the right to terminate or suspend the study at any time, however, this will be discussed between the relevant parties beforehand.

If the sponsor determines that any unanticipated adverse device effect presents an unreasonable risk to patients, the investigation will be terminated as soon as possible. Termination shall occur no later than 5 working days after the sponsor makes this determination and no later than 15 working days after the sponsor first receives notice of the unanticipated adverse device effect. Ethics committee approval will be obtained prior to resuming a terminated investigation.

	QMS Template	Doc ID: RMI-ROBOTECHO-CIP-002 Ver No: V2.0
	Clinical Investigation Protocol	

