APPENDIX 2 – Participant Experience Survey).

### 10.3 Adverse Events (AE), Adverse Device Events (ADE), Serious Adverse Events (SAE), Serious Adverse Device Event (SADE) and other Safety Reporting

The investigator and any qualified designees are responsible for detecting, documenting, and recording events that meet the definition of an AE/ADE or SAE and remain responsible for following up AEs that are serious, and considered related to the study intervention or study procedures.

To determine the safety of the RUAT echo, all AE/ADE/SAE/SADEs shall be recorded in the CRF and reported to the sponsor, ethics committee and TGA (if required) according to mandated timelines.

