#### 10.3.1 Definitions

The definitions applied for reporting adverse incidents for medical devices are those defined in ISO 14155:2020 Edition 3, July 2020.

Adverse Event (AE): Any undesirable clinical occurrence in a subject whether it is considered device related or not, that includes a clinical sign, symptom, or condition and/or an observation of an unintended technical performance or performance outcome of the device.

Adverse Device Event (ADE): A clinical sign, symptom or condition that is causally related to the presence of the device, or the performance of the device system.

An adverse event or an adverse device effect may be mild, moderate, or severe.

Serious Adverse Event (SAE): Any adverse medical occurrence that:

- Led to a death.
- Led to a serious deterioration in health of a patient user or other. This would include:
  - A life-threatening illness or injury.
  - A permanent impairment of body function or permanent damage to a body structure.
  - A condition requiring hospitalisation or prolongation of hospitalisation.
  - A condition requiring unnecessary medical or surgical intervention.
- Might have led to death or serious deterioration in health had suitable action or intervention not taken place. This includes:
  - Malfunction of a device such that it needs to be modified or temporarily/permanently taken out of service.
  - A factor (a deterioration in characteristics or performance) found on examination of the device.

Serious Adverse Device Event (SADE): A device-related serious adverse event.

Unanticipated Device Related Adverse Event: Any undesirable clinical occurrence in a subject considered device-related and not listed in the device technical manuals/Investigator’s Brochure.

	QMS Template	Doc ID: RMI-ROBOTECHO-CIP-002 Ver No: V2.0
	Clinical Investigation Protocol	

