### 10.3.4 Classification System

Investigators will be asked to assess the potential relationship of the adverse event to the ROBOT ECHO and/or to the procedure. For this study, each AE/ADE will be classified as device- or procedure-related. The following definitions will be used:

- **Procedure-related:** An adverse event that occurs due to the system application procedure. Commonly experienced events from an Echocardiogram include potential bruising, discomfort, focused pressure from the probe, lubricating gel may feel cold.
- **Device Related:** An adverse event that results from the presence or performance of the device or any other component of the system, for example if the RUAT robotic arm pushes too hard on the patient and fractures a rib.
- **Unknown:** If the adverse event cannot be determined to have a causal relationship with either the device or procedure, it will be classified as unknown.

The severity or intensity of each AE/ADE will be classified as per the below definitions:

- **Mild:** Patient is aware of event or symptom, but event/symptom is easily tolerated.
- **Moderate:** Patient experiences sufficient discomfort to interfere with or reduce their usual level of activity.
- **Severe:** Significant impairment of functioning; patient is unable to carry out usual activities.

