### 10.3.5 Investigator Reporting Responsibilities

The Investigator must immediately report all SAEs or SADEs (within 24 hours from time of learning of the event) to the sponsor using the supplied SAE/SADE reporting forms. Initial reports should be followed by detailed written reports. The investigator will determine whether the event was device related.

All SAE/SADEs are also captured and reported using the same terminology on the SAE/SADE Form in the Case Report Forms.

SAE/SADEs are emailed to:

Biointelect Pty Ltd Urgent Attention Safety Reporting [contact]
--

	QMS Template	Doc ID: RMI-ROBOTECHO-CIP-002 Ver No: V2.0
	Clinical Investigation Protocol	

The Investigator must also notify their respective HREC/s of any serious adverse outcomes immediately or as specified by the HREC guidelines.

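### Section 14 requires a stop only when the sponsor judges an unanticipated device effect an unreasonable risk; no passage of the protocol requires scanning to pause, or a decision to continue to be recorded, while a serious adverse device event is assessed

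*Protocol*

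**What the plan says.** **Mandatory stop (Section 14).** "If the sponsor determines that any unanticipated adverse device effect presents an unreasonable risk to patients, the investigation will be terminated as soon as possible". The stop must then come "no later than 5 working days after the sponsor makes this determination and no later than 15 working days after the sponsor first receives notice". Section 10.3.1 defines an unanticipated event as "Any undesirable clinical occurrence in a subject considered device-related and not listed in the device technical manuals" or the Investigator's Brochure.

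**Discretionary stop (Section 14).** Each of the sponsor, investigator, ethics committee and TGA "reserves the right to terminate or suspend the study at any time, however, this will be discussed between the relevant parties beforehand". No triggering event is named.

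**Reporting.** Section 10.3.5: "The Investigator must immediately report all SAEs or SADEs (within 24 hours from time of learning of the event) to the sponsor". The same section has the investigator notify the ethics committee of serious outcomes, at once or on the committee's own timetable. Section 10.3 adds that all events are "reported to the sponsor, ethics committee and TGA (if required) according to mandated timelines". Section 10.3.6 gives the sponsor 7 calendar days to tell the TGA of fatal or life-threatening unexpected device events, and 15 for other serious unanticipated ones. It also sends safety issues found among anticipated device events and other events to the TGA and ethics committees.

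**Emergency provisions.** Section 21.1 allows action against an immediate hazard before an amendment is approved. Section 21.2 allows deviation to protect a subject in an emergency.

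**The concern.** The mandatory rule is tied to a sponsor determination about one class of event. It does not tell the site whether to scan the next participant on the day after a serious device injury. Two gaps follow from the wording. A SADE that is already listed can never meet the trigger, however serious it is. For an unlisted SADE, nothing is required until the sponsor has made its determination.

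The question matters because the scan offers participants no clinical benefit: under Section 10.2, treatment has already been decided on the manual echo. Section 10.3.4 illustrates a device-related event with "for example if the RUAT robotic arm pushes too hard on the patient and fractures a rib". If such an injury happened, it would have happened despite the pressure limiter and the emergency stops in Section 12. Those controls alone could not then justify the next scan. At that point one would want a written reason for going on, and the order of events in Section 14, discussion first and suspension second, is the wrong way round.

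**Working it through.** **Step 1. Search for a hold.** The sections that could contain one, side by side:

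| Section | What it requires after a SADE | Pause or recorded decision? |
|---|---|---|
| 10.3, 10.3.5, 10.3.6 | Reports to sponsor, ethics committee and TGA | No |
| 10.3.1 | Counts as serious: "Malfunction of a device such that it needs to be modified or temporarily/permanently taken out of service" | No; it classifies an event and does not instruct a hold |
| 11.1.1 | Safety acceptable only with no device-related effects | No; a criterion for the end of the study |
| 11.5 | No formal interim analysis | No |
| 12 | Limiter, daily sensor check, emergency stops | No; they act within a scan |
| 13.2 | Withdrawal of the individual subject | No; does not affect the next subject |
| 14 | Termination on sponsor determination; otherwise a right to suspend | Only as described above |
| 15 | Monitoring visits about every 6 weeks | No |
| 21.1, 21.2 | Emergency action permitted | No; permitted, not required |

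**Step 2. What the Section 14 limits allow.** The protocol gives no figure for this. Inputs: 30 participants; recruitment over 2 months (Sections 3 and 8) or about 3 months (Section 8.1); limits of 5 and 15 working days (Section 14). Assumptions: even accrual and 5 working days a week.

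- Working days = months × (365.25/12) × (5/7): 43.5 for 2 months, 65.2 for 3 months.
- Scans per working day = 30/43.5 = 0.69, or 30/65.2 = 0.46.
- Within 15 working days: 10.3 (2 months) or 6.9 (3 months), so about 7 to 10 of 30.
- Within 5 working days: 3.4 or 2.3.

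Both limits apply together, so using the full 15 days requires a determination on working day 15 − 5 = 10 or later. An earlier determination shortens the period.

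**Step 3. Cost of a pause.** A pause of 5 working days (an assumed length) defers about 2 to 3 scans (2.3 to 3.4). How often it would happen is unknown, since the protocol gives no SADE rate. For assumed rates of a triggering event per participant, with at most one pause each:

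| Assumed rate | Chance of at least one pause in 30, 1 − (1 − p)^30 | Expected pauses, 30p | Expected delay at 5 working days each |
|---|---|---|---|
| 0.1% | 3.0% | 0.03 | 0.15 working days |
| 1% | 26.0% | 0.3 | 1.5 working days |
| 5% | 78.5% | 1.5 | 7.5 working days |

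The higher rate cannot be dismissed, because Section 10.3.1 counts some malfunctions as serious. Where a malfunction takes the device out of service, part of that delay would occur anyway.

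**The case against.** The strongest reply is that Section 14 contains no false or contradictory statement, and that this is a single site with three trained sonographers. The investigator who files the 24-hour report also holds a power to suspend. The ethics committee and TGA hear of serious events and can suspend too, including where the issue comes from anticipated events. Sections 21.1 and 21.2 let urgent action come first. The earlier study of 78 participants on the near-final device (Section 5.2) concluded that scans can be done safely, and the pressure limit is about half of a human operator's maximum (Section 12). The rib fracture is a definitional example, not a reported event. The criterion in 11.1.1 fails on any device-related effect, however mild, so it gives no special support to a rule for serious events.

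All of that stands, and it limits the point. It makes a serious event less likely and inaction after one less likely. It does not supply a duty to pause or a record that anyone considered pausing.

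A reader might infer that 7 to 10 people would be scanned after a serious injury, or that a listed SADE at participant 15 would expose all 15 remaining. The documents support neither as an expectation. The first needs a late determination, scanning at full pace and four inactive parties. The second needs either a listing in a Brochure or manual that is not shown, or a sponsor judgement that the risk is not unreasonable, in which case continuing is a decision and not an oversight. Nor can one say that no hold exists anywhere: the Brochure's risk analysis, the monitoring procedures and ISO 14155 are referred to, but their content is not available here.

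**Conclusion.** The point holds as a gap in a stated rule. Followed exactly, Section 14 leaves listed SADEs outside the mandatory stop, sets discussion ahead of any suspension, and asks for no record of why scanning went on. The ceilings are about 7 to 10 of 30 further scans under the 15-working-day limit and 2.3 to 3.4 under the 5-working-day limit. They rest on even accrual over the stated 2 to 3 months and on none of the four parties using its power to suspend. It would go too far to call the protocol unsafe as written: reporting is prompt, discretionary powers are broad and the within-scan controls are real. What is missing is an inexpensive, specific safeguard, and its priority is modest.

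**What to change.** Add to Section 14:

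> When the investigator becomes aware of any SADE, listed or not, or any SAE during or after a RUAT scan whose relation to the device is classed Unknown, RUAT scanning pauses at once, without prior discussion. It restarts only after the sponsor and principal investigator sign a dated decision recording the known or suspected cause (or that none was found), any corrective action, and why it is safe to resume.

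Keep the existing 5- and 15-working-day termination limits, and leave non-serious device effects under the present clause. Starting the pause at awareness avoids waiting for the 24-hour report. Including the Unknown class in Section 10.3.4 prevents an unsettled causality assessment from bypassing the rule. The second signature means that resuming does not rest on the sponsor alone. An unexplained fault does not block restart, and the pause has no minimum length.

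The cost is a protocol amendment, which Section 21.1 requires the ethics committee to approve before use, and, if the rule is triggered, the short deferral worked out above, with no scans lost. No new committee or reporting route is needed.

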## 15 Study Monitoring and Data Management

### 15.1 Study Monitoring

The sponsor has appointed Biointelect (a Contract Research Organisation) to manage and monitor the study to assure them of the quality conduct of the study and to act as the contact between the investigational site and the sponsor.

Prior to commencement of the study, the monitor will conduct an initiation visit to ensure that all site staff are aware of their study responsibilities, and that the study needs to be conducted in accordance with the study agreement, HREC approval and applicable ICH GCP guidelines.

Throughout the study, the monitor will maintain written and oral communication with the Investigator and their staff regarding the ongoing compliance of the study.

All monitoring and project management will be undertaken in accordance with ICH GCP and ISO 14155 utilising relevant SOPs.

### 15.2 Access to Study Records

The investigational site/investigator will ensure that there is direct access to source data and any associated trial documents required for trial monitoring, audits, HREC review and regulatory inspection. In addition, the investigational site staff must make themselves available to the sponsor, study monitor, HREC or regulatory agency as required.

### 15.3 Source Document and Data Verification

The study monitor will visit the investigational site periodically (approximately every 6 weeks or as deemed necessary) in accordance with the study monitoring plan. They shall:

- Meet with the investigator and any applicable site staff to discuss ongoing study compliance and data accuracy.
- Review all source documentation to verify CRF entries.
- Review the investigational site file and regulatory documentation.
- Ensure, where possible that CRF entries are corrected on site [in the first instance] should discrepancies be noted.
- Collect copies of documents and completed CRFs.

### 15.4 Data Management

Basic patient/participant demographic data and echo images shall be collected. Subjects who participate in the study are coded with a specific clinical investigation identification number. All subjects are registered in a subject identification list (subject enrolment and identification list) that connects the subject's name and hospital record number with a clinical investigation identification number. All data will be registered, managed, and stored in a manner that enables correct reporting, interpretation, verification, and participant privacy in compliance to the Privacy Act 1988, which includes the Australian Privacy Principles (APPs).

All participant data relating to the study will be recorded on printed CRFs or transmitted to the sponsor or designee electronically (e.g., imaging data). The investigator or study coordinator is responsible for verifying that data entries are accurate and correct by physically or electronically signing the CRF.

The ultrasound data will not be used for purposes other than the assessment of quality to indicate that the RUAT echo functions as intended.

## 16 Regulatory Requirements

### 16.1 Human Research Ethics Committee (HREC) Approval

Before the study begins, written approval will be obtained by the relevant HREC responsible for the investigational site.

### 16.2 Subject Informed Consent

Once identified by the research team as suitable for study participation, each potential participant shall provide informed consent to undergo an additional echocardiogram which shall be conducted using a robotic arm (RUAT echo).

The potential study participant will be approached in person via a member of the study team (study coordinator or research staff as delegated by the principal investigator) while on the ward as an inpatient or in clinic as an outpatient. The study coordinator or research staff will provide details of the study (verbally and via the information sheet as part of the Participant Informed Consent Form 'PICF'), and then provide invitation for participation, free from coercion and pressure and with as much time as required for the potential participant to consider participating as well as the opportunity to ask questions.

It is the investigator's responsibility to ensure that each subject gives written informed consent to participate in the study prior to any study specific procedures at the time of screening. Each subject will be provided with a Patient Information and Consent Form. The investigator and/or assigned study coordinator will explain the nature of the study, its purpose, procedures, expected duration, and the potential benefits, risks and inconveniences in participation as outlined in the Participant Information Sheet. The subject will be given adequate time to decide whether they wish to participate and ask questions. On acceptance of participation, they will voluntarily sign and date (in their own handwriting) the information and consent form. The investigator and/or study nurse will also sign and date the same form. A signed and dated copy will be provided to the subject. The other copy will be maintained in the study file.

The subjects will be informed of their rights to privacy but will be made aware that the study data will be submitted to the sponsor and possibly to drug regulatory authorities for review and evaluation. They will be informed also that the study monitor may inspect their medical records to verify the accuracy and completeness of the study records and results.

The subjects will be informed of their right to withdraw from the study at any time without prejudice.

